## **Biochemical Parameters**

### **GCF Periostin levels**

When the GCF Periostin data were examined, the difference between the groups was found to be statistically significant at the beginning ( $p=0.003$ ). In terms of periodontal disease, the amount of GCF Periostin in the P group was found to be significantly lower than in the H group ( $p=0.007$ ), while there was no statistically significant difference between the SP group and the SH group.

When evaluated in terms of smoking, it was observed that the GCF Periostin amount of the SP group was significantly higher than the P group ( $p=0.021$ ). There was no significant difference between the SH and H groups ( $p>0.05$ ).

A statistically significant difference was found between the groups on the 15th day ( $p<0.001$ ). When examined in terms of periodontal disease in the post-hoc analysis, it was found that the amount of GCF Periostin in the P group was significantly lower than in the H group, as at the beginning ( $p=0.002$ ). It was determined that there was no statistically significant difference between the SP group and the SH group. When evaluated in terms of smoking, it was observed that the GCF Periostin amount of the SP group was significantly higher than the P group ( $p=0.003$ ).

However, on the 30th day, it was determined that there was no statistically significant difference between the groups.

In the in-group evaluation of the change with treatment on a time basis, it was found that the GCF Periostin level in the SP group decreased over time ( $p<0.001$ ). In post-hoc analyzes, this decrease was observed to be significant between all times ( $p=0.009$ (0-15.days, respectively),  $p=0.001$ . (day 0-30) and  $p=0.003$ (day 15-30)). In the P group, there was no statistically significant difference in the evaluations of the 0th day, 15th day and 30th day within the group ( $p>0.05$ ).

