buccodistal, linguo/palatomesial, midgingual/palatal, linguo/palatodistal regions) with using using millimetric (mm) calibrated University of North Carolina (UNC) (Hu-Friedy, Chicago, Illinois, USA). And up-to-date panoramic radiographs were taken from all patients on the day of the examination to determine periodontal status. After the clinical and radiographic evaluations, the participants were asked to come for GCF sample and treatment 1 day after the clinical evaluations, since bleeding may occur during probing.

From the patients in the SP and P groups, GCF samples were obtained from the 5 deepest pockets before the treatment, on the 15th and 30th days after the treatment. GCF samples were obtained taken from 5 randomly selected teeth with GI=0 PI=0 and SPD  $\leq 3$  from healthy individuals in the SH and H groups.

GCF samples were acquired by intrasulcular technique from selected pockets. Before sampling, the sites were isolated with cotton rolls, saliva and supragingival plaque were removed by cotton pellets, if present. Standardized filter paper strips (Peripaper® Oraflow Inc. New York, USA) were placed in the pocket for 30 seconds. Strips contaminated with blood or saliva were discarded. The absorbed GCF volume was measured with a precalibrated Periotron 8000 instrument (PeriotronR 8000, Pro Flow Inc., Amityville, NY, USA). Then, the strips were placed in sterile 0.5 ml Eppendorf (Eppendorf AG, Hamburg, Germany) tubes. Eppendorf tubes were stored at -80°C in Ondokuz Mayıs University Faculty of Medicine Department of Biochemistry until ELISA analysis. GCF samples were converted to an actual volume ( $\mu$ L) by reference to a standard curve.

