### **Treatment and Follow-up Protocol**

Patients in the SH and H groups were advised to come for routine controls by not applying any periodontal treatment. However for patients in the SP and P groups, non-surgical periodontal treatment was applied as full mouth debridement protocol in a single session, after the GCF samples were collected from selected pockets.

The periodontitis patients were called again on the 15th and 30th days after the treatment. First of all, the GCF sampling process was repeated from the teeth whose GCF sample was collected before. Then, clinical examination parameters (PI, GI, BOP, PD and CAL) values were measured again and recorded.

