### **Statistical analysis**

SPSS for Windows Ver. for statistical analysis and graphics. 22.0 (SPSS Inc., Chicago, ILL, USA) and MS-Excel 2016 programs were used. Statistical significance level was accepted as p<0.05.

The normal distribution of the data in our study was evaluated with the Shapiro-Wilks test. The mean±standard deviation was used for the descriptive statistics for the normally distributed variables, and the median (min-max) value for the non-normally distributed variables. While examining the distribution of the gender variable in the groups, the result of the Chi-Square test was evaluated.

OneWay ANOVA test was applied to the variables showing normal distribution in the comparison of the data between groups. In post-hoc analyses, homogeneously distributed data according to Levene variance homogeneity test were evaluated with Tukey test, and data that were not homogeneously distributed were evaluated with Tamhane T2 test. Variables that did not show normal distribution were evaluated with the Kruskal-Wallis test. Bonferroni corrected Mann-Whitney U test was used in order to determine the group that caused the difference in the variables with a significant difference as a result of the Kruskal-Wallis test.

Paired-Sample T Test and Repeated Measured Analysis of Variance were used for the variables showing normal distribution in the evaluation of the within-group changes according to time. Significant differences as a result of analysis of variance were examined with Bonferroni, one of the multiple comparison tests. Variables that did not show normal distribution were analyzed with the Friedman test. The Wilcoxon test was used to determine the group that caused the difference in the variables with a significant difference as a result of the Friedman test.

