## **RESULTS**

### **Demographic Findings**

The distributions of gender and age of the groups were as follows: SP (seven male and four female subjects; mean age:  $40,9 \pm 9,28$  years); P (three male and eight female subjects; mean age:  $41 \pm 12,30$  years); SH (seven male and four female subjects; mean age:  $30,27 \pm 9,99$  years); H (three male and eight female subjects; mean age:  $26,36 \pm 4,20$  years).

The study groups were evaluated in terms of age and gender, and a significant difference was found between the groups in terms of mean age ( $\chi^2=16,567$ ; p=0.001). There was no

significant difference in terms of gender ( $\chi^2=0.364$ ;  $p=0.546$ ). The mean age of the H group was lower than the mean age of the patients in the SP ( $Z=18,000$ ;  $p=0.006$ ) and P groups ( $Z=16.682$ ;  $p=0.014$ ). It was determined that the mean age of the individuals was similar ( $Z=3,682$ ;  $p=1,000$ ) between group H and group SH.

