### **Sample Teeth Clinical Findings**

GCF was taken from the 5 deepest pockets measured before the treatment from the patients in the SP and P groups of the study groups before the treatment, on the 15th and 30th days after the treatment. GCF was taken from 5 randomly selected teeth with  $GI=0$   $PI=0$  and  $PD \leq 3$  from individuals in SH and H groups.

All clinical parameters (PI, GI, BOP, PD, CAL and GCF volume) of these selected teeth were analyzed statistically. There was a significant difference between the groups in all clinical parameters before treatment. The measurements of SP and P groups were higher than the healthy groups ( $p<0.05$ ).

There was a significant difference between the groups in terms of BOP, PD, CAL and GCF volumes on the 15th and 30th days after treatment.

There was no statistically significant difference between the periodontitis groups (SP-P) and healthy groups (SH-H) on the 0th, 15th and 30th days in terms of smoking ( $p>0.05$ ).

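### No direct SP–P comparison is planned for days 15 and 30, so day-30 periostin has only an overall null and differential change is untested

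*Combined protocol and SAP*

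**What the plan says.** **Who is sampled.** The opening section gives three GCF sampling times for SP and P: before treatment, day 15 and day 30. For SH and H it says "GCF samples were obtained taken from 5 randomly selected teeth" and names no repeat time. Treatment and Follow-up Protocol adds "The periodontitis patients were called again on the 15th and 30th days after the treatment"; SH and H are only advised to attend routine controls.

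**What is tested.** Statistical analysis compares groups by one-way ANOVA (then Tukey or Tamhane T2) or by Kruskal-Wallis. Bonferroni-corrected Mann-Whitney tests are used "in order to determine the group that caused the difference in the variables with a significant difference as a result of the Kruskal-Wallis test". Time courses are tested within each group. There is no follow-up test restricted to SP and P, and no test comparing their changes.

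**What is reported.**
- Periostin, day 15: overall p<0.001; "the amount of GCF Periostin in the P group was significantly lower than in the H group, as at the beginning" (p=0.002); SP and SH not different; SP above P (p=0.003; p=0.021 on day 0).
- Periostin, day 30: "However, on the 30th day, it was determined that there was no statistically significant difference between the groups". Nothing is given for SP against P.
- Periostin over time: SP fell in every interval; P showed no significant change.
- IL-17A: no group difference at any time; P rose by day 30 and SP did not change significantly.

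**The concern.** The results use SP against P as the smoking comparison in periodontitis. After treatment it is also the only contrast between groups documented as sampled on the same days. Yet it appears only as one of several pairs in a comparison where 22 of 44 values (50%) seem to come from untreated people seen once. For periostin it is not reported on the day the overall test is null.

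Two questions then go unanswered. How far apart are SP and P in periostin on day 30? And did they change by different amounts? The second is suggested by the periostin and IL-17A time courses, but one significant and one non-significant within-group p-value do not test a difference between the two changes.

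**Working it through.** **1. Are SH and H in the follow-up tests?** For periostin on day 15, yes: P–H and SP–SH results are given. For day 30 it is an inference. Sample Teeth Clinical Findings reports a "significant difference between the groups in terms of BOP, PD, CAL and GCF volumes on the 15th and 30th days after treatment", and also "no statistically significant difference between the periodontitis groups (SP-P) and healthy groups (SH-H) on the 0th, 15th and 30th days" with respect to smoking. If SP and P did not differ, the overall differences must involve the healthy values. The day-30 periostin sentence has the same form as the day-15 one.

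**2. Are pairs examined only after a significant overall test?** This is explicit for Kruskal-Wallis and implied for ANOVA by the term post-hoc. The reporting fits: SP–P periostin p-values appear on days 0 and 15, when the overall test was significant, and not on day 30.

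**3. How many pairs are corrected for?** The plan does not say. The age comparisons in Demographic Findings allow a check if the printed Z values are read as mean-rank differences over all 44 subjects:
- SE = sqrt(44 × 45/12 × 2/11) = 5.477
- H–SP: 18.000/5.477 = 3.286, raw p = 0.00102; × 6 = 0.0061 (reported 0.006)
- H–P: 16.682/5.477 = 3.046, raw p = 0.00232; × 6 = 0.0139 (reported 0.014)
- H–SH: 3.682/5.477 = 0.672; × 6 exceeds 1 (reported 1.000)

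Multiplying by 3 would give 0.003 and 0.007, which do not match. Six pairs fit for age; carrying that over to periostin is an inference.

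**4. Observed SP–P gap needed for significance**, in SD units. Inputs: 11 per group (opening section) and the 0.05 level (Statistical analysis); two-sided tests and equal SDs are assumed.
- Direct t-test, 0.05: 2.086 × sqrt(2/11) = 0.89
- Direct t-test, 0.025 (two days): 2.423 × sqrt(2/11) = 1.03
- Tukey, four groups: 3.791/sqrt(11) = 1.14
- Overall F-test: sqrt(2.839 × 3/11/0.5) = 1.24 if SH and H lie midway; sqrt(2.839 × 3/11/0.75) = 1.02 if both lie at the level of SP or of P

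**5. Chance of declaring a true SP–P gap.** Simulated normal data, with SH and H midway or level with one periodontitis group. The gap is assumed, because the documents give no periostin SDs.

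| Route | True gap 1.0 SD |
|---|---|
| Direct t-test, 0.05 | 61% |
| Direct t-test, 0.025 | 48% |
| Tukey, no overall test required | 38% |
| Overall F-test, then Tukey | 35–38% |

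The step from 61% to 38% (23 points) is the effect of correcting for six pairs. Requiring the F-test first takes a further 0.5–2.5 points. Against the 0.025 direct test, the total shortfall is about 10–13 points (48 − 38 to 48 − 35). Among datasets where the direct 0.025 test is significant, the F-test is not in about 9–20%.

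**The case against.** - **The overall test costs little power.** This stands. A reader might infer that requiring a significant four-group test hid a real day-30 difference. The figures do not support that: nearly all of the loss comes from correcting for six pairs, a defensible choice with four groups.
- **The periostin pattern fits convergence.** This stands. SP began higher and fell while P showed no significant change, so a small day-30 gap is plausible. The documents hold no data to decide it.
- **The report never says smokers and non-smokers are alike.** Correct; it states only the absence of significance. The gap is in what was estimated, not in a false claim.
- **SH and H may have been resampled.** Possible. Both clinical findings sections mention SH–H for days 0, 15 and 30, although the methods describe no such visits. The documents need to settle this.
- **SP–P is reported elsewhere.** Partly. The clinical parameters have SP–P statements on all three days, and IL-17A and IL-17E have a general statement of no smoking difference. The missing day-30 result is specific to periostin. No biomarker estimate or interval is given for any group or day, so that part is reporting style.
- **A single healthy sample is a valid reference** for P–H or SP–SH. Agreed; it needs only a label.

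**Conclusion.** The point holds as a gap in planning and reporting that should be fixed. No direct SP–P comparison and no comparison of their changes is planned for follow-up. Day-30 periostin therefore has no SP–P result, and the differing time courses in periostin and IL-17A are not tested against each other.

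It does not follow that the day-30 null is wrong or produced by the order of testing. The size, 48–61% direct against 35–38% by the four-group route, rests on an assumed 1.0 SD gap, normal data with equal SDs, and a six-pair correction inferred from the age results. That SH and H entered the day-30 periostin test is likely but inferred. Confidence is medium.

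**What to change.** 1. Keep the four-group test for day 0.
2. For each biomarker, report SP minus P on days 15 and 30, and the SP–P difference in change from day 0 (or a day-0-adjusted comparison), each with a 95% confidence interval and tests at 0.05/2 = 0.025, whatever the four-group test shows. For data already analysed, label these post hoc.
3. Give these estimates beside the overall day-30 periostin and IL-17A statements.
4. Label post-treatment P–H and SP–SH as comparisons with a single-visit healthy sample and limit SH–H to day 0. If repeat healthy samples exist, document them; step 2 still applies.

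**Cost.** Re-analysis only, with no new patients or visits. The SP–P false-positive rate per follow-up day rises from about 1% or less to 2.5%. Nothing corrects across the three biomarkers, and follow-up would use a different correction from day 0, so p-values are not comparable between days. The estimates and intervals should carry the interpretation.

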### **GCF IL-17A levels**

In the analysis of GCF IL-17A values, no statistically significant difference was found between the groups in terms of both periodontal disease and smoking at any time ( $p>0.05$ ).

In the evaluation of the change with non-surgical periodontal treatment according to time, no statistically significant difference was found in the GCF IL-17A levels of the SP group between the baseline, the 15th day and the 30th day ( $p>0.05$ ). only in the P group, it was found that the GCF IL-17A level increased on the 30th day, with a statistically significant difference ( $p<0.05$ ). Significant differences were found between day 0 and day 30, and day 15 and day 30 in post-hoc analyzes ( $p=0.009$ ,  $p=0.005$ , respectively).

### **GCF IL-17E levels**

In the analysis of GCF IL-17E levels, there was no statistically significant difference between the groups in terms of both periodontal disease and smoking at any time ( $p>0.05$ ).

In the evaluation of the change with non-surgical periodontal treatment, there was no statistically significant change in GCF IL-17E levels at any time in both the SP group and the P group ( $p>0.05$ ).
